### **8.3. Adverse Events, Serious Adverse Events, and Other Safety Reporting**

Timely, accurate, and complete reporting and analysis of safety information, including AEs, SAEs, and product quality complaints (PQCs), from clinical studies are crucial for the protection of participants, investigators, and the sponsor, and are mandated by regulatory agencies worldwide.

The sponsor has established Standard Operating Procedures in conformity with regulatory requirements worldwide to ensure appropriate reporting of safety information; all clinical studies conducted by the sponsor or its affiliates will be conducted in accordance with those procedures.

AEs will be reported by the participant (or, when appropriate, by a caregiver, surrogate, or the participant's legally acceptable representative) for the duration of the study.

Anticipated events related to HS exacerbation will be recorded and reported as described in Section 10.2.

Further details on AEs, SAEs and PQC can be found in Section 10.5.

### **8.3.1. Time Period and Frequency for Collecting Adverse Event and Serious Adverse Event Information**

#### **All Adverse Events**

All adverse events and special reporting situations, whether serious or non-serious, will be reported from the time a signed and dated ICF is obtained until completion of the participant's last study-related procedure, which may include contact for follow-up of safety.

#### **Serious Adverse Events**

All serious adverse events, as well as PQC, occurring during the study must be reported to the appropriate sponsor contact person by study-site personnel within 24 hours of their knowledge of the event.

Serious adverse events, including those spontaneously reported to the investigator within 12 weeks after the last administration of study intervention, must be reported using the Serious Adverse Event Form. The sponsor will evaluate any safety information that is spontaneously reported by an investigator beyond the time frame specified in the protocol.

A possible Hy's law Case is defined by the occurrence of alanine transaminase/aspartate transaminase  $\geq 3$  x upper limit of normal (ULN), alkaline phosphatase  $< 2$  x ULN together with total bilirubin  $\geq 2$  x ULN or international normalized ratio  $> 1.5$  (if measured). Any possible Hy's Law case is considered an important medical event and should be reported to the sponsor in an expedited manner, even before all other possible causes of liver injury have been excluded.

Information regarding SAEs will be transmitted to the sponsor using the Serious Adverse Event Form and Safety Report Form of the CRF, which must be completed and reviewed by a physician from the study site and transmitted to the sponsor within 24 hours. The initial and follow-up reports of an SAE should be transmitted electronically or by facsimile (fax). Telephone reporting should be the exception and the reporter should be asked to complete the appropriate form(s) first.

### **8.3.2. Method of Detecting Adverse Events and Serious Adverse Events**

Care will be taken not to introduce bias when detecting AEs or SAEs. Open-ended and nonleading verbal questioning of the participant is the preferred method to inquire about AE occurrence.

### **Solicited Adverse Events**

Solicited AEs are predefined local at the injection site and systemic events for which the participant is specifically questioned and which are noted by participants in their diary (see Section 8).

### **Unsolicited Adverse Events**

Unsolicited AEs are all AEs for which the participant is not specifically questioned in the participant diary.

#### **8.3.3. Follow-up of Adverse Events and Serious Adverse Events**

The investigator is obligated to perform or arrange for the conduct of supplemental measurements and evaluations as medically indicated to elucidate the nature and causality of the AE, SAE or PQC as fully as possible. This may include additional laboratory tests or investigations, histopathological examinations, or consultation with other health care professionals. AEs, including pregnancy, will be followed by the investigator as specified in Section 10.5.

#### **8.3.4. Regulatory Reporting Requirements for Serious Adverse Events and Anticipated Events**

The sponsor assumes responsibility for appropriate reporting of AEs to the regulatory authorities. The sponsor will also report to the investigator (and the head of the investigational institute where required) all suspected unexpected serious adverse reactions (SUSARs). The investigator (or sponsor where required) must report SUSARs to the appropriate Independent Ethics Committee/Institutional Review Board (IEC/IRB) that approved the protocol unless otherwise required and documented by the IEC/IRB. A SUSAR will be reported to regulatory authorities unblinded. Participating investigators and IEC/IRB will receive a blinded SUSAR summary, unless otherwise specified.

An anticipated event is an AE that commonly occurs in the study population independent of exposure to the drug under investigation. For the purposes of this study the following SAEs will be considered anticipated events:

- Worsening of HS

These anticipated events will be periodically analyzed in aggregate by the sponsor during study conduct. The sponsor will prepare a safety report in narrative format if the aggregate analysis indicates that the anticipated event occurs more frequently in the intervention group than in the control group and the sponsor concludes there is a reasonable possibility that the drug under investigation caused the anticipated event.

The plan for monitoring and analyzing the anticipated events is specified in a separate Anticipated Events Safety Monitoring Plan. The assessment of causality will be made by the sponsor's unblinded safety assessment committee.

The sponsor assumes responsibility for appropriate reporting of the listed anticipated events according to the requirements of the countries in which the studies are conducted.

### **8.3.5. Pregnancy**

All initial reports of pregnancy in female participants or partners of male participants must be reported to the sponsor by the study-site personnel within 24 hours of their knowledge of the event using the appropriate pregnancy notification form. Abnormal pregnancy outcomes (e.g., spontaneous abortion, fetal death, stillbirth, congenital anomalies, ectopic pregnancy) are considered SAEs and must be reported using a serious adverse event reporting form. Any participant who becomes pregnant during the study must discontinue further study intervention (see Section 7.1).

Follow-up information regarding the outcome of the pregnancy and any postnatal sequelae in the infant will be required.

### **8.3.6. Adverse Events of Special Interest**

Any newly identified malignancy or case of active TB occurring after the first study intervention administration(s) in participants participating in this clinical study must be reported by the investigator according to the procedures in Section 10.5. Investigators are also advised that active TB is considered a reportable disease in most countries. These events are to be considered serious only if they meet the definition of an SAE.

## **8.4. Pharmacokinetics and Immunogenicity**

Blood samples will be collected for the measurement of serum bermekimab concentrations and antibodies to bermekimab at the time points presented in the SoA.

At visits in which serum bermekimab concentration and/or antibodies to bermekimab will be evaluated, 1 venous blood sample of sufficient volume should be collected, and each serum sample should be divided into 3 aliquots: 1 for serum concentration of bermekimab and a back-up. Each serum sample will be divided into 3 aliquots: 1 for serum concentration of bermekimab, 1 for antibodies to bermekimab, and 1 back-up.

Blood samples should also be collected at the final visit or at the Early Termination Visit from participants who are discontinued from intervention or withdrawn from the study. Blood samples collected for serum bermekimab concentrations may also be used for exploratory biomarker analyses.

A random venous blood sample for population PK analysis will be collected from all participants on any day between Weeks 2 to 12, except on the days of the scheduled study visits. Additionally, this blood sample must be collected at least 24 hours prior to or after the actual time of study intervention administration. Each population PK serum sample will be divided into 2 aliquots: 1 for serum concentration of bermekimab and a back-up.

The exact dates and times of blood sample collection must be recorded in the laboratory requisition form. See the laboratory manual for further information regarding collection, handling, and shipment of biological samples. Genetic analyses will not be performed on these serum samples. Participant confidentiality will be maintained.

### **Pharmacokinetic Analytical Procedures**

Serum samples will be analyzed to determine serum bermekimab concentrations using a validated, specific, and sensitive immunoassay method under the supervision of the sponsor. The sponsor, or its designee, under conditions in which the participants' identity remains blinded, will assay these samples.

### **Immunogenicity Analytical Procedures**

The detection and characterization of antibodies to bermekimab will be performed using a validated, drug-tolerant immunoassay method by or under the supervision of the sponsor. Serum samples will be screened for antibodies binding to bermekimab and the titer of confirmed positive samples will be reported. Antibodies to bermekimab may be further characterized and/or evaluated for their ability to neutralize the activity of bermekimab.

## **8.5. Genetics and Pharmacogenomics**

Genetic and epigenetic variation can be an important contributory factor to interindividual differences in drug disposition and response and may also serve as a marker for disease susceptibility and prognosis. Pharmacogenomic research consists of the analysis of one or more candidate genes or of the analysis of markers throughout the genome (as appropriate) in relation to bermekimab or HS clinical endpoints. The goal of the pharmacogenomic/epigenomic component is to explore factors that may influence the PK, PD, efficacy, or tolerability of bermekimab and to evaluate genetic factors previously reported to be associated with HS or help identify new associations. These DNA samples may be used to help address emerging issues and to enable the development of safer, more effective, and more precisely applied therapies.

A pharmacogenomic blood sample will be collected from participants who consent separately to this component of the study to allow for pharmacogenomic research, as necessary (where local regulations permit). Genotyping or sequencing techniques will be used to assess variation genome-wide. Participation in pharmacogenomic research is optional.

## **8.6. Biomarkers**

Biomarker samples will be collected to evaluate the PD and mechanism of action of bermekimab or help to explain interindividual variability in clinical outcomes or may help to identify population subgroups that respond differently to the intervention. The goal of the biomarker analyses is to evaluate the PD of and aid in evaluating the intervention-clinical response relationship.

Biomarker assessments will include the evaluation of relevant markers in blood and wound exudate (when present) for all participants. Genetic analysis, skin biopsies, FibroTx Transdermal Patch analysis (when kits are available), and skin swabs will also be collected from participants who consent to this optional part of the study. The samples will be used to better understand the biology of HS; to provide biological assessment of the response of participants to treatment with bermekimab; to analyze differences between responders and nonresponders; and to determine if the markers can be used to classify participants as potential responders prior to treatment. Blood samples will be separated into serum, plasma, and peripheral blood mononuclear cells (PBMCs)

for biomarker analysis. Samples for serum biomarkers, flow cytometry and gene expression from blood will be collected at time points according to the SoA (Section 1.3). Instructions for the collection and shipment of these samples are found in the Laboratory Reference Manual and Biopsy Collection Manual.

### **8.6.1. Skin Biomarkers**

Wound exudates (from all participants when present) and FibroTx Patch assessments (from participants who consent to this optional part of the study and when kits are available) will be collected at time points specified in the SoA (Section 1.3). Protein analysis will be done to monitor the PD effect and to understand mechanism of action of bermekimab.

Participants may participate in collection of biopsies (nodule and ultrasound guided deep tunnel biopsy) and/or skin swabs for microbiome analysis in this optional part of the study.

Skin biopsy samples will be collected from participants that consent to this optional part of the study at time points specified in the SoA (Section 1.3). At baseline, biopsy samples will be collected from both lesional (nodule) and adjacent non-lesional areas (10 cm away from the lesional nodule). At subsequent time points (Week 16 and Week 32 in Part 1, and Week 12 and Week 32 in Part 2), only lesional areas will be sampled. At Week 16 in Part 1 and Week 12 in Part 2, 2 nodules and 1 tunnel (if present) will be sampled. If a participant consents to undergoing Week 32 biopsies, 1 nodule and 1 tunnel biopsy will be sampled at Week 32. Gene expression analysis of skin biopsy samples will be performed to investigate differential gene expression during treatment compared to baseline to explore PD, mechanism of action, and differences in responders versus nonresponders. Proteomic analysis will be used to explore the target occupancy and the treatment effect on the affected skin. All skin biopsies and sampling should be completed after completion of the disease severity assessments by the investigator/sub-investigator. In addition, the tissue biopsies may be analyzed for histological readouts and immunohistochemistry to explore the effects of study intervention on cellular composition within skin tissue. Skin swabs will be collected to study the effect of intervention on microbiome composition on affected skin.

### **8.6.2. Serum Biomarkers**

Serum samples will be collected from all participants at time points specified in the SoA (Section 1.3). Potential circulating factors to be evaluated may include cytokines and other inflammatory markers (eg, IL-6, IL-8, TNF $\alpha$ , SAA), and other categories of biomarkers potentially associated with HS or related to the mechanism of action of bermekimab.

### **8.6.3. Plasma Biomarkers**

Plasma samples will be collected from all participants at time points specified in the SoA (Section 1.3). Potential circulating factors to be evaluated may include complements and other biomarkers potentially associated with HS or related to the mechanism of action of bermekimab.

### **8.6.4. Flow Cytometry Analysis**

Whole blood samples will be collected from all participants at time points specified in the SoA (Section 1.3), and PBMC will be isolated. Flow cytometry analysis of blood cell samples will be

utilized to monitor the effects of bermekimab on circulating immune cell populations. Cell surface markers such as, but not limited to, those for T cell subsets (eg, Th1, Th2), dendritic cells, and B cells will be assessed.

### **8.6.5. Gene Expression Analysis in Whole Blood**

Whole blood samples will be collected from all participants at time points specified in the SoA (Section 1.3). Total RNA will be isolated and used for differential gene expression analyses to better understand the pathologic mechanisms involved in HS and to potentially identify a treatment response signature to bermekimab.

### **Stopping Analysis**

Biomarker analyses are dependent upon the availability of appropriate biomarker assays and clinical response rates. Biomarker analysis may be deferred or not performed, if during or at the end of the study, it becomes clear that the analysis will not have sufficient scientific value for biomarker evaluation, or if there are not enough samples or responders to allow for adequate biomarker evaluation. In the event the study is terminated early or shows poor clinical efficacy, completion of biomarker assessments is based on justification and intended utility of the data.

### **8.7. Health Economics**

Health economics parameters are not evaluated in this study.

## **9. STATISTICAL CONSIDERATIONS**

Statistical analysis will be done by the sponsor or under the authority of the sponsor. A general description of the statistical methods to be used to analyze the efficacy and safety data is outlined below. Specific details will be provided in the SAP.

### **9.1. Statistical Hypotheses**

The primary hypothesis of this study is that bermekimab is superior to placebo as assessed by the proportion of participants achieving Hidradenitis Suppurativa Clinical Response (HiSCR50) at Week 16 in Part 1, and at Week 12 in Part 2.

- HiSCR50 is defined as at least 50% reduction in total abscess and inflammatory nodule counts (AN count) with no increase in abscess count and no increase in draining fistula count relative to baseline.

### **9.2. Sample Size Determination**

This study is designed to enroll approximately 250 or 300 participants, in order to provide sufficient data to have adequate power for the primary endpoint.

The sample size of 250 or 300 participants was also chosen in order to:

- Have sufficient power to detect a difference between the bermekimab groups and the placebo group for the primary endpoint of the proportion of participants achieving HiSCR50 at Week 16 between the bermekimab treatment group and the placebo group in Part 1 and at

Week 12 between bermekimab treatment groups and placebo group combining Part 1 and Part 2.

- Have an adequate confidence level for the treatment difference between the bermekimab high dose group and the adalimumab group in HiSCR50 at Week 16 in Part 1.
- Provide greater precision for the interim analysis efficacy analysis with more participants in the bermekimab 1050 mg, adalimumab, and placebo groups.

The assumptions for the sample size and power calculations specified below were mainly based on the clinical data from the 77474462HDS2002 (PT-047) Phase 2 clinical study and from 2 adalimumab (Humira) Phase 3 clinical studies M11-313 (PIONEER I) and M11-810 (PIONEER II) that evaluated the safety and efficacy of adalimumab in the treatment of adult participants with moderate to severe HS.

The response rates observed in the 77474462HDS2002 (PT-047) study for HiSCR50 at Week 12/Week 16 were 55%/57% (bermekimab qw group), 44%/52% (bermekimab q2w group), and 44%/44% (placebo group), respectively. In addition, the HiSCR50 response rates in the adalimumab Phase 3 Studies M11-313 and M11-810 at Week 12 were 42% vs 26% and 59% vs 28% in the adalimumab weekly and placebo groups, respectively.

Comparisons between treatment groups at Week 16 with Part 1 data (all comparisons are at a 2-sided type 1 error rate of 0.10; [Table 1](#) and [Table 2](#))

- For comparison between bermekimab with placebo using data from Part 1 only for the primary endpoint at Week 16, the study sample size provides 83% power to detect a 25% treatment difference (50% vs 25%) with 50 participants per arm.
- Greater than 99% power to detect a 40% (75% vs 35%) difference between the bermekimab 1050 mg treatment group (n=50) and the placebo group (n=50).
- From comparison between adalimumab with placebo using data from part 1 only for the primary endpoint, the study sample size provides 83% power to detect a 25% (50% vs 25%) treatment difference with 50 participants per arm.

No formal comparisons will be performed between the bermekimab 1050 mg qw group and the adalimumab group from Part 1, however the treatment difference and its 2-sided 80% CI for the primary endpoint at Week 16 between these 2 groups will be provided. A sample size of 50 participants in each of the treatment groups will produce a 2-sided 80% CI for the treatment difference with a width of approximately 29%.

Comparisons between treatment groups at Week 12 with combining Part 1 and Part 2 data

Assuming HiSCR50 response rates at Week 12 are 25% to 35% for placebo and 50% to 75% for the bermekimab groups, respectively; based on these assumptions, approximately 250 participants across Part 1 and Part 2 are planned to be randomized to the placebo (n=75), bermekimab 700 mg qw to q2w (n=50), bermekimab 1050 mg qw to q2w (n=50), and bermekimab 1050 mg qw (n=75) treatment groups. Comparisons between the bermekimab groups and the placebo groups will be based on data combining Part 1 and Part 2.

For comparisons between bermekimab groups with placebo combining Part 1 and Part 2 for the primary endpoint, bermekimab 1050 mg qw and 1050 mg qw → q2w groups will be grouped together as bermekimab 1050 mg group (n=125) and 700 mg qw → q2w group will be denoted as bermekimab 700 mg group, the study sample size provides:

- At least 87% power to detect a 25% treatment difference between the bermekimab 700 mg treatment group (n=50) and the placebo group (n=75).
- 97% power to detect a 25% (50% vs 25%) treatment difference between the bermekimab 1050 mg treatment group (n=125) and the placebo group (n=75).
- Greater than 99% power to detect a 40% (75% vs 35%) difference between the bermekimab 1050 mg treatment group (n=125) and the placebo group (n=75) or between 700 mg treatment group (n=50) and the placebo group (n=75).

in HiSCR50 at Week 12 combining Part 1 and Part 2 based on a 2-sample Z-test at a Type I error rate of 0.10 (2-sided; [Table 3](#)).

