#### Comparisons between treatment groups at Week 12 with combining Part 1 and Part 2 data

Assuming HiSCR50 response rates at Week 12 are 25% to 35% for placebo and 50% to 75% for the bermekimab groups, respectively; based on these assumptions, approximately 250 participants across Part 1 and Part 2 are planned to be randomized to the placebo (n=75), bermekimab 700 mg qw to q2w (n=50), bermekimab 1050 mg qw to q2w (n=50), and bermekimab 1050 mg qw (n=75) treatment groups. Comparisons between the bermekimab groups and the placebo groups will be based on data combining Part 1 and Part 2.

For comparisons between bermekimab groups with placebo combining Part 1 and Part 2 for the primary endpoint at Week 12, the study sample size provides:

- At least 87% power to detect a 25% treatment difference between the bermekimab 700 mg treatment groups (n=50) and the placebo group (n=75).
- 97% power to detect a 25% (50% vs 25%) treatment difference between the bermekimab 1050 mg treatment group (n=125) and the placebo group (n=75).
- Greater than 99% power to detect a 40% (75% vs 35%) difference between the bermekimab 1050 mg treatment group (n=125) and the placebo group (n=75) or between 700 mg treatment groups (n=50) and the placebo group (n=75).

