#### 9.4.2.1.3. Primary Endpoint Analysis

In the primary efficacy analysis, data from all randomized participants who received at least 1 administration of study intervention will be analyzed according to their assigned treatment group.

In this primary analysis, the proportion of participants who achieve a HiSCR50 at Week 16 in Part 1, and at Week 12 based on the combined data from Part 1 and Part 2 will be summarized for each treatment group. To address the primary objective, a CMH chi-squared statistic stratified by baseline Hurley stage status (II, III) at an alpha level of 0.1 will be used for each of the comparisons between bermekimab treatment groups and placebo group.

There will be 3 comparisons for the primary analyses. The proportion of participants who achieve HiSCR50 will be compared between bermekimab treatment groups and the placebo group based on the fixed-sequence testing approach. To maintain an overall Type I error rate of 0.1, the 3-pairwise comparisons will be performed sequentially at a two-sided alpha level of 0.1 in the following order:

1. Bermekimab 1050 mg group versus Placebo at Week 12 based on the combined data from Part 1 and Part 2
2. Bermekimab 1050 mg group versus Placebo at Week 16 based on the data from Part 1
3. Bermekimab 700 mg group versus Placebo at Week 12 based on the combined data from Part 1 and Part 2

With the pre-specified sequential analyses, whenever a prior comparison is not significant at a two-sided alpha level of 0.1, the remaining treatment group comparisons will be considered nonsignificant and the p-values from the remaining treatment group comparison will be considered nominal.

In addition, the comparison between adalimumab and placebo for the primary endpoint at Week 16 in Part 1 will also be performed.

This method is to control the type-1 error at 10% level or less and will only be implemented for the primary efficacy analysis. The study will be considered positive if one of the hypotheses is tested as significant at a 2-sided alpha level of 0.10.

To examine the robustness of the primary endpoint analysis, additional analyses will be conducted using different missing data approaches; these analyses will be described in the SAP. In addition, sensitivity analyses will be performed for the primary endpoint using the per-protocol population, which includes participants who are generally compliant with the protocol.

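### The 87-89% power stated for 700 mg versus placebo is single-comparison power; as third test in the fixed sequence it is about 68-77% if 1050 mg also has a 25-point effect

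*Protocol*

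**What the plan says.** Protocol Section 9.2 gives the power for 700 mg as "At least 87% power to detect a 25% treatment difference between the bermekimab 700 mg treatment group (n=50) and the placebo group (n=75", and says that the Week 12 figures are "based on a 2-sample Z-test at a Type I error rate of 0.10" (two-sided). Table 3 lists 89%, 87% and 87% for a 25-point difference at placebo rates of 25%, 30% and 35%. The Synopsis has the same claim, "At least 87% power to detect a 25% treatment difference between the bermekimab 700 mg treatment groups (n=50) and the placebo group (n=75", and SAP Section 3 reprints the text and the table.

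For the other two primary comparisons at 25 points, Section 9.2 states "97% power to detect a 25% (50% vs 25%) treatment difference between the bermekimab 1050 mg treatment group (n=125) and the placebo group (n=75" (Week 12, combined data) and "83% power to detect a 25% treatment difference (50% vs 25%) with 50 participants per arm" (Week 16, Part 1). Table 1 gives 81% for the Week 16 comparison at placebo rates of 30% and 35%.

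Section 9.4.2.1.3 then ties the three together: "the 3-pairwise comparisons will be performed sequentially at a two-sided alpha level of 0.1 in the following order". The order is 1050 mg at Week 12 (combined), 1050 mg at Week 16 (Part 1), 700 mg at Week 12 (combined). The rule is that "whenever a prior comparison is not significant at a two-sided alpha level of 0.1, the remaining treatment group comparisons will be considered nonsignificant".

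**The concern.** The 700 mg power is calculated as if that comparison were tested by itself, but the plan never tests it by itself. It comes after two 1050 mg tests, and the second of these uses only the 50 participants per arm from Part 1. When both doses have a 25-point effect, 700 mg cannot be declared significant more often than the Week 16 test succeeds, which Table 1 puts at 81-83%. A stated floor of 87% is above that ceiling.

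At stake is the reader's view of the design. Section 9.2 implies an 11-13% chance of missing a 25-point effect of 700 mg, and it hides what it costs to place the smaller Part 1 test ahead of the 700 mg test.

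**Working it through.** **Inputs.** Two-sided alpha 0.10 (z = 1.645). Group sizes from Section 9.2: 1050 mg 125, placebo 75, 700 mg 50 at Week 12; 50 and 50 at Week 16. By part (Sections 6.3 and 9.2): placebo 50 + 25; 1050 mg 50 + 25 (qw) + 50 (qw→q2w); 700 mg 50, all in Part 2. Rates: "Assuming HiSCR50 response rates at Week 12 are 25% to 35% for placebo and 50% to 75% for the bermekimab groups". The 25-point rows are 25/50, 30/55 and 35/60.

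**Step 1: reproduce the plan's figures.** For a Z-test with pooled variance under the null,

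power = Φ[(d − 1.645·s0)/s1], with s0 = √{p̄(1−p̄)(1/n1 + 1/n0)} and s1 = √{p1(1−p1)/n1 + p0(1−p0)/n0}.

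At 50% versus 25%:

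- Test 3 (50 vs 75): p̄ = 0.35, s0 = 0.0871, s1 = 0.0866; (0.25 − 0.1432)/0.0866 = 1.233; power 89.1%.
- Test 1 (125 vs 75): p̄ = 0.406, s0 = 0.0717, s1 = 0.0671; (0.25 − 0.1180)/0.0671 = 1.968; power 97.5%.
- Test 2 (50 vs 50): p̄ = 0.375, s0 = 0.0968, s1 = 0.0935; (0.25 − 0.1593)/0.0935 = 0.970; power 83.4%.

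| Placebo rate | Test 1 | Test 2 | Test 3 alone | Table 3, 700 mg |
|---|---|---|---|---|
| 25% | 97.5% | 83.4% | 89.1% | 89% |
| 30% | 97.0% | 81.9% | 87.9% | 87% |
| 35% | 96.8% | 81.2% | 87.2% | 87% |

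Dropping the decimals gives the printed values in Tables 1 and 3. The stated 87-89% is therefore reproduced as stand-alone power.

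**Step 2: bound.** P(all three significant) ≤ P(test 2 significant). With 25 points for 1050 mg this is 83.4%, 81.9% and 81.2%. If the tests were independent, the product would be 0.975 × 0.834 × 0.891 = 72.5% at a placebo rate of 25%, and 69.9% and 68.5% at 30% and 35%.

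**Step 3: the sequence itself.** The tests are not independent: they share placebo participants, and tests 1 and 2 share the Part 1 participants. The three tests were therefore simulated with these overlaps, with at least 100,000 trials per scenario. The within-participant correlation between Week 12 and Week 16 response is not in the documents, so it was varied from 0 to 1. With a 25-point effect for both doses, and for 1050 mg at both weeks:

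| Placebo rate | Stated | Power in the sequence (correlation 0 to 1) |
|---|---|---|
| 25% | 89% | 74-77% |
| 30% | 87% | 70-74% |
| 35% | 87% | 68-72% |

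Passing tests 1 and 3 without test 2 has 85-88% power, so nearly all of the loss comes from the Week 16 test.

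**Step 4: sensitivity to the 1050 mg effect.** 700 mg held at 25 points, correlation 0.5, range over the three placebo rates:

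| 1050 mg effect | Power to declare 700 mg |
|---|---|
| 25 points | 70-75% |
| 30 points | 80-84% |
| 35 points | 85-87% |
| 40 points | 87-89% |

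Correlation moves the result by about 3 to 4 points over its whole range. The 1050 mg effect moves it by up to about 17.

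**The case against.** The strongest reply is that nothing is miscalculated. Section 9.2 names a two-sample Z-test and Table 3 is laid out by pair of groups, so a careful reader can tell that the figures are pairwise. That stands: a reader might infer an arithmetic mistake, and Step 1 shows there is none. What is missing is a label and the power of the procedure that would be used.

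A reader might also infer that 700 mg power can never exceed 81-83%. The documents do not support that without a condition. The 700 mg sentence fixes only the 700 mg effect, the assumed bermekimab range runs to 75%, and Protocol Section 4.3 reports an exposure-response trend that favours higher exposure. If 1050 mg is clearly better than 700 mg, the loss shrinks and is about half a point at 40 points. Even so, a large 1050 mg effect cannot be taken for granted. Section 9.2 gives one response range for all bermekimab groups, and the earlier placebo-controlled study that it cites showed differences for the weekly regimen of 11 points at Week 12 (55% vs 44%) and 13 points at Week 16 (57% vs 44%).

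A third tempting inference is that the interim decisions reduce the power further. Their criteria are in a separate interim plan, so the effect cannot be sized. Once Part 2 has opened it could even go the other way, because that decision rests on the same Part 1 Week 16 endpoint as test 2.

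Finally, the practical weight is low. Section 9.4.2.1.3 counts the study as positive on any one significant hypothesis, so success turns on test 1, and the 700 mg arm was optional. The SAP records termination for futility, covers Part 1 only, and contains neither a 700 mg test nor the fixed sequence. All of that stands.

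**Conclusion.** The point holds in a conditional form. The 87-89% is correct as single-comparison power, but it is not the chance that the declared procedure finds 700 mg significant. If both doses have a 25-point effect, and 1050 mg has it at both weeks, that chance is about 68-77%. This is 12 to 19 points below the stated figures, with a miss probability of about 23-32% rather than 11-13%. At a 30-point 1050 mg effect it is 80-84%, still below the stated floor; at 35 points it is 85-87%; at 40 points the difference is negligible.

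These results assume the planned group sizes with no dropout, the plan's unstratified Z-test instead of the Hurley-stratified CMH test, and Part 2 run with the 700 mg arm. The interim decisions are not modelled. A reader might infer that the issue affects a conclusion of the trial; it does not, because no 700 mg comparison remains in the SAP.

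**What to change.** In Protocol Section 1.1, Section 9.2 and Table 3, and in SAP Section 3, label the 87-89% as power for a single comparison. Beside it, give the power to declare 700 mg under the fixed sequence, for stated 1050 mg effects (for example 25, 30, 35 and 40 points) and a stated Week 12/Week 16 correlation, or a range of correlations. The 1050 mg effect must appear with any such figure, because it is the main driver.

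The cost is a few lines and a less favourable figure at the smaller 1050 mg effects. Enrolment, alpha and testing order stay as they are, and no remaining analysis is affected.
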